3.3 Inclusion of Women and Minorities

Both men and women of all races and ethnic groups are eligible for this trial.

4. REGISTRATION PROCEDURES

4.1 Investigator and Research Associate Registration with CTEP

4.1.1 CTEP Registration Procedures

Food and Drug Administration (FDA) regulations and National Cancer Institute (NCI) policy require all investigators participating in any NCI-sponsored clinical trial to register and to renew their registration annually. To register, all individuals must obtain a Cancer Therapy Evaluation Program (CTEP) Identity and Access Management (IAM) account (<https://ctepcore.nci.nih.gov/iam>). In addition, persons with a registration type of Investigator (IVR), Non-Physician Investigator (NPIVR), or Associate Plus (AP) must complete their annual registration using CTEP's web-based Registration and Credential Repository (RCR) (<https://ctepcore.nci.nih.gov/rcc>).

RCR utilizes five person registration types.

- IVR — MD, DO, or international equivalent;
- NPIVR — advanced practice providers (*e.g.*, NP or PA) or graduate level researchers (*e.g.*, PhD);
- AP — clinical site staff (*e.g.*, RN or CRA) with data entry access to CTSU applications such as the Roster Update Management System [RUMS], OPEN, Rave, acting as a primary site contact, or with consenting privileges;
- Associate (A) — other clinical site staff involved in the conduct of NCI-sponsored trials; and
- Associate Basic (AB) — individuals (*e.g.*, pharmaceutical company employees) with limited access to NCI-supported systems.

RCR requires the following registration documents:

Documentation Required	IVR	NPIVR	AP	A	AB
FDA Form 1572	✓	✓			
Financial Disclosure Form	✓	✓	✓		
NCI Biosketch (education, training, employment, license, and certification)	✓	✓	✓		
GCP training	✓	✓	✓		
Agent Shipment Form (if applicable)	✓				
CV (optional)	✓	✓	✓		

An active CTEP-IAM user account and appropriate RCR registration is required to access all CTEP and Cancer Trials Support Unit (CTSU) websites and applications. In addition, IVRs and NPIVRs must list all clinical practice sites and Institutional Review Boards (IRBs) covering their practice sites on the FDA Form 1572 in RCR to allow the following:

- Added to a site roster
- Assigned the treating, credit, consenting, or drug shipment (IVR only) tasks in OPEN;
- Act as the site-protocol Principal Investigator (PI) on the IRB approval; and
- Assign the Clinical Investigator (CI) role on the Delegation of Tasks Log (DTL).

In addition, all investigators acting as the Site-Protocol PI (investigator listed on the IRB approval), consenting/treating/drug shipment investigator in OPEN, or as the CI on the DTL must be rostered at the enrolling site with a participating organization.

Additional information is located on the CTEP website at <https://ctep.cancer.gov/investigatorResources/default.htm>. For questions, please contact the **RCR Help Desk** by email at [contact].

4.2 CTSU Registration Procedures

This study is supported by the NCI CTSU.

4.2.1 IRB Approval

For CTEP and Division of Cancer Prevention (DCP) studies open to the National Clinical Trials Network (NCTN) and NCI Community Oncology Research Program (NCORP) Research Bases after March 1, 2019, all U.S.-based sites must be members of the NCI Central Institutional Review Board (NCI CIRB). In addition, U.S.-based sites must accept the NCI CIRB review to activate new studies at the site after March 1, 2019. Local IRB review will continue to be accepted for studies that are not reviewed by the CIRB, or if the study was previously open at the site under the local IRB. International sites should

continue to submit Research Ethics Board (REB) approval to the CTSU Regulatory Office following country-specific regulations.

Sites participating with the NCI CIRB must submit the Study Specific Worksheet (SSW) for Local Context to the CIRB using IRBManager to indicate their intent to open the study locally. The NCI CIRB's approval of the SSW is automatically communicated to the CTSU Regulatory Office, but sites are required to contact the CTSU Regulatory Office at [contact] to establish site preferences for applying NCI CIRB approvals across their Signatory Network. Site preferences can be set at the network or protocol level. Questions about establishing site preferences can be addressed to the CTSU Regulatory Office by email or calling [name].

In addition, the Site-Protocol Principal Investigator (PI) (i.e. the investigator on the IRB/REB approval) must meet the following criteria in order for the processing of the IRB/REB approval record to be completed:

- Holds an active CTEP status;
- Active status at the site(s) on the IRB/REB approval (*applies to US and Canadian sites only*) on at least one participating organization's roster;
- If using NCI CIRB, active on the NCI CIRB roster under the applicable CIRB Signatory Institution(s) record;
- Includes the IRB number of the IRB providing approval in the Form FDA 1572 in the RCR profile;
- Lists all sites on the IRB/REB approval as Practice Sites in the Form FDA 1572 in the RCR profile; and
- Holds the appropriate CTEP registration type for the protocol.

Additional Requirements

Additional site requirements to obtain an approved site registration status include:

- An active Federal Wide Assurance (FWA) number
- An active roster affiliation with the Lead Protocol Organization (LPO) or a participating organization (PO); and
- An active roster affiliation with the NCI CIRB roster under at least one CIRB Signatory Institution (US sites only); and
- Compliance with all protocol-specific requirements (PSRs).

4.2.2 Downloading Site Registration Documents

Download the site registration forms from the protocol-specific page located on the CTSU members' website. Permission to view and download this protocol and its supporting documents is restricted to the institutions and its associated investigators and staff on a participating roster. To view/download site registration forms:

- Log in to the CTSU members' website (<https://www.ctsu.org>) using your CTEP-IAM username and password;
- Click on *Protocols* in the upper left of your screen;
- Either enter the protocol number in the search field at the top of the protocol tree, or
- Click on the By Lead Organization folder to expand, then select *CITN*, and protocol *CITN-14*.
- Click on *Documents*, *Protocol Related Documents*, and use the *Document Type* filter and select *Site Registration* to download and complete the forms provided. (Note: For sites under the CIRB, IRB data will load automatically to the CTSU.)

4.2.3 Submitting Regulatory Documents

Submit required forms and documents to the CTSU Regulatory Office using the Regulatory Submission Portal on the CTSU members' website.

To access the Regulatory Submission Portal log in to the CTSU members' website, go to the *Regulatory* section and select *Regulatory Submission*.

Institutions with patients waiting that are unable to use the Regulatory Submission Portal should alert the CTSU Regulatory Office immediately by phone or email: [name], or [contact] in order to receive further instruction and support.

4.2.4 Checking Site Registration Status

Site registration status may be verified on the CTSU members' website.

- Click on *Regulatory* at the top of your screen;
- Click on *Site Registration*; and
- Enter your 5-character CTEP Institution Code and click on Go;
 - Additional filters are available to sort by Protocol, Registration Status, Protocol Status, and/or IRB Type.

Note: The status shown only reflects institutional compliance with site registration requirements as outlined within the protocol. It does not reflect compliance with protocol requirements for individuals participating on the protocol or the enrolling investigator's status with the NCI or their affiliated networks.

4.3 Delegation of Tasks Log (DTL)

Each site must complete a protocol-specific Delegation of Tasks Log (DTL) using the DTL application in the Delegation Log section on the CTSU members' website. The Clinical Investigator (CI) is required to review and electronically sign the DTL prior to the site receiving an approved site registration status and enrolling patients to the study. To maintain an approved site registration status the CI must re-sign the DTL at least annually and when a new version of the DTL is released; and to activate new task

assignments requiring CI sign-off. Any individual at the enrolling site on a participating roster may initiate the site DTL. Once the DTL is submitted for CI approval, only the designated DTL Administrators or the CI may update the DTL. Instructions on completing the DTL are available in the Help Topics button in the DTL application and include a Master Task List, which describes DTL task assignments, CI signature, and CTEP registration requirements.

4.4 Patient Enrollment

4.4.1 OPEN

The Oncology Patient Enrollment Network (OPEN) is a web-based registration system available to users on a 24/7 basis. OPEN is integrated with CTSU regulatory and roster data and with the LPOs registration/randomization systems or the Theradex Interactive Web Response System (IWRs) for retrieval of patient registration/randomization assignment. OPEN will populate the patient enrollment data in NCI's clinical data management system, Medidata Rave.

Requirements for OPEN access:

- A valid CTEP-IAM account;
- To perform enrollments or request slot reservations: Must be on an LPO roster, ETCTN corresponding roster, or participating organization roster with the role of Registrar. Registrars must hold a minimum of an Associate Plus (AP) registration type;
- If a Delegation of Tasks Log (DTL) is required for the study, the registrars must hold the OPEN Registrar task on the DTL for the site; and
- Have an approved site registration for the protocol prior to patient enrollment.

To assign an Investigator (IVR) or Non-Physician Investigator (NPIVR) as the treating, crediting, consenting, drug shipment (IVR only), or receiving investigator for a patient transfer in OPEN, the IVR or NPIVR must list the IRB number used on the site's IRB approval on their Form FDA 1572 in RCR. If a DTL is required for the study, the IVR or NPIVR must be assigned the appropriate OPEN-related tasks on the DTL.

Before accessing OPEN, site staff should verify the following:

- Patient has met all eligibility criteria within the protocol stated timeframes; and
- All patients have signed an appropriate consent form and Health Insurance Portability and Accountability Act (HIPAA) authorization form (if applicable).

Note: The OPEN system will provide the site with a printable confirmation of registration and treatment information. Please print this confirmation for your records.

Access OPEN at <https://open.ctsu.org> or from the OPEN link on the CTSU member's website. Further instructional information is on the OPEN section of the CTSU website at

<https://www.ctsu.org> or at <https://open.ctsu.org>. For any additional questions contact the CTSU Help Desk at [name] or [contact].

Patient enrollment for this study will be facilitated using the Slot Reservation System in conjunction with the registration system in OPEN. Prior to discussing protocol entry with the patient, all site staff must use the CTSU OPEN Slot Reservation System to ensure that a slot on the protocol is available to the patient. Once a slot reservation confirmation is obtained, site staff may then proceed to enroll the patient to this study.

4.5 General Guidelines

After registration, patients should begin protocol treatment within 5 business days. Issues that would cause treatment delays should be discussed with the PI. If a patient does not receive protocol therapy after registration, the patient's registration on the study may be canceled. The Clinical Research Site (CRS) must notify the CITN Coordinating Center of cancellations as soon as possible.

Except in very unusual circumstances, each participating institution will order DCTD-supplied agents directly from CTEP.

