2. BACKGROUND

2.1 Study Disease(s)

The proposed clinical trial is a phase II, open-label, multicenter, randomized study of the administration of Atezolizumab (MPDL3280A) monotherapy or in combination with Recombinant Human IL-7 (CYT107) in patients with advanced or metastatic urothelial carcinoma.

Urothelial carcinoma is the fifth most common malignancy in the United States [[Siegel 2014](#)]. Advanced or metastatic urothelial carcinoma carries a grim prognosis and has limited treatment options [[von der Maase 2000](#)]. The immunogenicity of urothelial bladder cancer (UBC) was first demonstrated by the successful use of BCG for non-muscle invasive bladder cancer and carcinoma in situ [[Kamat 2001](#)]. More recently, antibodies blocking PD-1/PD-L1 signaling in endogenous T cells have induced dramatic and durable clinical responses in patients with metastatic urothelial carcinoma, further highlighting urothelial carcinoma as a compelling target for T-cell immunotherapy [[Powles 2014](#); [Plimack 2017](#)]

Early studies with impressive response rates and durable responses led to regulatory approval of 5 different PD-1/PD-L1 antibodies. This includes atezolizumab, durvalumab, nivolumab, avelumab, and pembrolizumab. Survival outcomes have been assessed in randomized phase 3 trials with atezolizumab and pembrolizumab. Pembrolizumab was successful in demonstrating improved overall survival outcomes over taxane or vinflunine chemotherapy in the post-platinum-treated advanced or metastatic UBC setting [[Bellmunt 2017](#)]. Atezolizumab also demonstrated an overall survival benefit over taxane or vinflunine chemotherapy in the post-platinum-treated advanced or metastatic UBC setting in the intention to treat analysis (presentation abstract). However, the primary study endpoint was based on an enrichment biomarker approach based on PD-L1 immunohistochemical staining, and that enrichment approach failed, as the biomarker was very clearly prognostic for improved outcomes in both arms, but not predictive for improved response to atezolizumab.

We now attempt to demonstrate improved clinically meaningful outcomes with the addition of CYT107 to atezolizumab over atezolizumab alone for patients with advanced or metastatic urothelial carcinoma.

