5. TREATMENT PLAN

This is a phase II trial of atezolizumab (MPDL3280A) plus recombinant human IL-7 (CYT107) in patients with locally advanced or metastatic urothelial carcinoma. The trial follows a randomized, controlled trial design, with an initial 'Safety Run-In' phase designed to evaluate the acute safety profile of the investigational treatment combination.

During the Safety Run-In phase, 6 patients will be assigned to the experimental arm (atezolizumab + CYT107) with staggered enrollment. This will be accomplished with an initial 3 patient enrollment. All adverse events will be assessed by the Toxicity Evaluation Committee. If 0-1 patient experiences a protocol-defined DLT (refer to [Section 5.2](#)) after completion of the 4-week DLT window, an additional 3 patients will be enrolled. Once all 6 patients have completed the 4-week DLT window, the Toxicity Evaluation Committee will again assess all adverse events. If, at any time, 2 or more patients experience a protocol-defined DLT, further enrollment into the trial will be suspended.

If the treatment combination of the experimental arm demonstrates an acceptable safety profile in the Safety Run-In (one or fewer patient experiences a protocol-defined DLT), randomized enrollment into the trial will begin.

Patients will be randomly assigned to either the control arm (atezolizumab monotherapy) or experimental arm (atezolizumab + CYT107) of the trial.

The first 6 subjects enrolled in the run-in phase of the study will have PK sampling done at baseline (prior to CYT107 administration), and at week 4 prior to CYT107 administration and at 2 hours, 4 hours and 6 hours after the fourth CYT107 administration.

Anti-drug antibody testing (ADA testing) will be done on all subjects who receive CYT107. Testing will be done at baseline (prior to CYT107 administration) and at week 8, (1 month after

the last CYT107 administration.) Any subject who develops binding antibodies will be further tested for the presence of anti-CYT107 neutralizing antibodies.

Randomization in the OPEN system may be performed up to 5 business days before initiation of study treatment to allow for clinical site logistics.

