13.3 Sample Size/Accrual Rate

During the Safety Run-In phase, 6 patients will be assigned to the experimental arm (atezolizumab + CYT107) with staggered enrollment (refer to [Section 5](#) for details). The AEs will be assessed by the Toxicity Evaluation Committee. If, at any time, 2 or more patients experience a protocol-defined DLT (refer to [Section 5.2](#)), further enrollment into the trial will be suspended.

If the treatment combination of the experimental arm demonstrates an acceptable safety profile in the Safety Run-In (1 or fewer patient experiences a protocol-defined DLT), randomized enrollment into the trial will begin.

A total of 54 patients will be enrolled in this study; 6 patients in the Safety Run-In and 48 patients in the randomized portion of the study. The expected accrual is 4 patients per month total at approximately 8 CITN sites. A study with 48 randomly assigned patients (1:1 randomization) will meet the following statistical parameters: $H_{\text{null}} = 14.8\%$; $H_{\text{alt}} = 45\%$; one-sided alpha of 0.10; power 88%.

The interim futility analysis will be conducted when 24 randomized patients have their first disease assessment and survival information. The futility analysis is based on an O'Brien-Fleming boundary, and the futility boundary will be considered to be crossed when the difference of ORR in the experimental arm – ORR in the control arm is less than -0.0063. Under the null hypothesis, the probability of crossing the futility boundary is 48.2%.

Safety Population: All patients who receive at least 1 dose of the investigational regimen will be considered evaluable for safety and included in the overall safety analysis. For the Safety Run-in phase, in the absence of a DLT, patients must complete the full 28-day DLT window period to be considered evaluable for DLTs. Patients who discontinue from the study before the completion of the full 28-day DLT window for reasons other than the occurrence of a DLT (e.g., withdrawal of consent, rapid tumor progression, death due to rapid tumor progression, AE that does not meet DLT criteria) will not be considered evaluable for DLTs and will be replaced.

Efficacy Population: The efficacy analysis will be conducted on all randomized patients, based upon the intent-to-treat population.

PLANNED ENROLLMENT REPORT

Racial Categories	Ethnic Categories		Totals
	Not Hispanic or Latino	Hispanic or Latino	

	Female	Male	Female	Male	
American Indian/ Alaska Native	1	2			3

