13.6.2 Evaluation of Response

All patients included in the study must be assessed for response to treatment, even if there are major protocol treatment deviations or if they are ineligible. Each patient will be assigned one of the following categories: (1) complete response, (2) partial response, (3) stable disease, (4) progressive disease, (5) early death from malignant disease, (6) early death from toxicity, (7) early death because of other cause, or (9) unknown (not assessable, insufficient data). [Note: By arbitrary convention, category 9 usually designates the "unknown" status of any type of data in a clinical database.]

All of the patients who met the eligibility criteria (with the possible exception of those who received no study medication) should be included in the main analysis of the

response rate. Patients in response categories 4-9 should be considered to have a treatment failure (disease progression). Thus, an incorrect treatment schedule or drug administration does not result in exclusion from the analysis of the response rate. Precise definitions for categories 4-9 will be protocol specific.

All conclusions should be based on all eligible patients. Subanalyses may then be performed on the basis of a subset of patients, excluding those for whom major protocol deviations have been identified (early death due to other reasons, early discontinuation of treatment, major protocol violations, *etc.*). However, these subanalyses may not serve as the basis for drawing conclusions concerning treatment efficacy, and the reasons for excluding patients from the analysis should be clearly reported. The 95% confidence intervals should also be provided.

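### Sections 4.5 and 13.6.2 let randomized but untreated patients drop out after the open-label arm is known, against the all-randomized population of 13.3

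*Combined protocol and SAP*

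**What the plan says.** Section 4.5 of the protocol expects treatment to begin within 5 business days of registration and continues: "If a patient does not receive protocol therapy after registration, the patient's registration on the study may be canceled". The one duty it attaches is notification: "The Clinical Research Site (CRS) must notify the CITN Coordinating Center of cancellations as soon as possible". It does not separate run-in registrations from randomized ones.

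Section 5 sets the timing: "Randomization in the OPEN system may be performed up to 5 business days before initiation of study treatment". Section 4.4.1 describes OPEN as linked to other systems "for retrieval of patient registration/randomization assignment" and adds: "The OPEN system will provide the site with a printable confirmation of registration and treatment information". Section 2.1 describes the trial as open-label.

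Section 13.3 fixes the efficacy population: "The efficacy analysis will be conducted on all randomized patients, based upon the intent-to-treat population". Section 13.6.2 says something different. There, eligible patients, "with the possible exception of those who received no study medication) should be included in the main analysis" of the response rate. Section 13 states that no separate SAP will be issued, so no other document settles the matter.

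**The concern.** Intention to treat protects the comparison because nothing that happens after allocation can decide who is counted. Here a patient can be randomized, the site and patient can learn the arm, treatment may not start, and the registration can then be cancelled. If the decision not to start is related to the arm and to prognosis, the patients who remain are no longer the groups that randomization created. Section 13.6.2 opens a second route to the same result: an untreated patient who stays registered can still be left out of the main response analysis.

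The stakes are the randomized comparisons of ORR, PFS and OS. With 24 patients per arm, one patient is 1/24 = 4.2% of an arm.

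**Working it through.** **1. The plan's own figure.** Section 13.3 gives 48 randomized patients 1:1, ORR 14.8% against 45%, one-sided alpha 0.10 and power 88%. With unpooled variance:

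- SE = √(0.148×0.852/24 + 0.45×0.55/24) = 0.1248
- (0.45 − 0.148)/0.1248 = 2.421, and 2.421 − 1.282 = 1.139
- Power = Φ(1.139) = 87.3%, close to the stated 88%

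Exact enumeration of the planned Cochran-Mantel-Haenszel (CMH) test gives 85.6% power and a type I error of 0.102.

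**2. The rules side by side**

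| Question | Section | Answer |
|---|---|---|
| Can an untreated patient's registration be cancelled? | 4.5 | Yes; randomized patients not excepted |
| Can the arm be known by then? | 2.1, 4.4.1, 5 | Yes; open-label, up to 5 business days before treatment |
| Who is analysed for efficacy? | 13.3 | All randomized |
| Who is in the main response analysis? | 13.6.2 | Eligible patients, the untreated possibly left out |
| What follow-up is set for never-treated patients? | 5.6 | None specific; off-treatment imaging is tied to stopping treatment |
| Do the replacement rules help? | 5.7, 13.3 | No; they cover only DLT evaluability in the run-in |

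**3. Effect on the test.** Section 13.2.1 names the CMH test and Section 13.4 has no randomization strata, so I use a single 2×2 table. Let b be experimental responders, m all responders, n_E and n_C the arm sizes, and N their sum:

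z = (b − E)/√V, with E = n_E·m/N and V = n_E·n_C·m·(N − m)/[N²(N − 1)].

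The number of cancellations is an assumption (1 to 3 of 48), and each removed patient is taken to be a non-responder.

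| Experimental | Control | E | V | z | One-sided p |
|---|---|---|---|---|---|
| 8/24 | 4/24 | 6.000 | 2.298 | 1.319 | 0.094 |
| 8/24 | 4/23 | 6.128 | 2.282 | 1.240 | 0.108 |
| 8/24 | 4/22 | 6.261 | 2.262 | 1.156 | 0.124 |
| 6/24 | 3/24 | 4.500 | 1.867 | 1.098 | 0.136 |
| 6/22 | 3/24 | 4.304 | 1.847 | 1.248 | 0.106 |
| 6/21 | 3/24 | 4.200 | 1.833 | 1.330 | 0.092 |
| 9/24 | 5/24 | 7.000 | 2.532 | 1.257 | 0.104 |
| 9/23 | 5/24 | 6.851 | 2.510 | 1.356 | 0.088 |

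Losing control non-responders can turn a positive result negative. Losing experimental non-responders can do the reverse. One removal is enough in the closest cases.

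**4. How often that would happen.** I enumerated all outcomes at 24 per arm and removed two non-responders from one arm. With 14.8% in both arms, the verdict changes in 1.1% of trials (control removals) or 2.6% (experimental removals). With 14.8% against 45%, it changes in 3.6% or 4.0%.

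**5. Power and imputation.** Exact power with patients removed is 84.4% (one per arm), 83.0% (two per arm) and 82.7% (four control only), against 85.6% with none.

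If they are kept and counted as non-responders, two per arm gives 83.0% power and leaves type I error at 0.102. Unequal losses do not: two control patients give type I error 0.125 and power 88.4%, three control patients give type I error 0.138, and two experimental patients give 0.082 and 79.4%.

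**The case against.** The strongest reply is that Section 4.5 is administrative and takes nobody out of the analysis. Cancellation is optional. Read literally, Section 13.3 still counts a cancelled patient as randomized. Section 13.6.2 requires every patient included in the study to be assessed, has a category for unknown response, and treats that category as failure. An intention-to-treat ORR could then be computed from the randomization list.

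Much of this stands, and it rules out four stronger inferences that a reader might draw:

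- **A cancelled patient leaves no study record.** Section 4.4.1 says OPEN populates enrollment data in Rave. Nothing orders data to be deleted or follow-up to stop.
- **The site decides alone.** The sentence is passive. The site's stated duty is to notify, and causes of delay are to be discussed with the PI.
- **The slot is re-used.** Section 4.4.1 describes slot reservation only as a step before enrollment.
- **Sections 4.5 and 13.3 cannot both be followed.** They can, if the option to cancel is not used or a cancelled patient is still counted.

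A reader might also infer from the withdrawn US indication (Section 2.2.1) that control patients would refuse more often. Both arms receive atezolizumab, and the documents give no refusal rate by arm. Control refusals by non-responders would also make a positive result harder to reach, not easier.

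What the reply does not answer is whether a patient with a cancelled registration still counts as included in the study. Section 13.6.2 does not close the gap, because its exception for untreated patients points the other way. Nor can a randomization list supply PFS or OS data that nobody was told to collect.

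**Conclusion.** The concern holds as an unreconciled conflict. Two stated rules, in 4.5 and 13.6.2, permit a randomized patient to be excluded after the arm is known, while 13.3 promises that all randomized patients are analysed. This is more than missing detail, because the exclusion is expressly allowed.

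The likely size is modest. Power falls by at most about 3 points for up to four removals. Two one-sided removals of non-responders change the verdict in roughly 1% to 4% of trials under the plan's response rates, so the p-value examples are near-threshold illustrations and not expected results. The harm is possible selection by arm.

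These sizes rest on an assumed number of cancellations and on the removed patients being non-responders; the documents give neither. The six run-in patients are not affected, since Section 13.2 reports them separately.

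**What to change.** **Section 4.5.** State that cancellation applies only to non-randomized (run-in) registrations. A randomized patient who does not start therapy stays in the 13.3 population and, unless consent is withdrawn, is followed for disease status and survival. A missing response counts as non-response. Never-treated patients are reported by arm with reasons.

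**Section 13.6.2.** Delete the exception for patients who received no study medication from the randomized comparison, or limit it to a sensitivity analysis. Changing 4.5 alone would leave this second route open.

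**Cost.** A few sentences, a small number of extra follow-up contacts and a slightly lower ORR. Counting untreated patients as non-responders is not neutral when their numbers differ by arm (type I error 0.125 with two control patients, 0.082 with two experimental). Actual response outcomes should therefore be collected where possible, with imputation as the fallback.
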